8.2.2. Proportion of patients with relapse of AF within 5 min (IRAF)

The proportion of patients with relapse of AF within 5 min (IRAF) following pharmacological or DC cardioversion will be presented by treatment and analysed using a logistic regression model. The model will include treatment, and duration of current AF episode.

In addition the same analysis will be done for the proportion of patients with relapse of AF within 5 min (IRAF) following pharmacological cardioversion only.

8.2.3. Proportion of patients in SR

The proportion of patients in SR after start of infusion at different timepoints (3 h \pm 1 h, 24 h \pm 2 h and 30 days \pm 5 days after start of infusion) will be presented by treatment group and analysed using a logistic regression model. The model will include treatment and duration of current AF episode.

This document is confidential.

9. Analysis of Pharmacokinetics

All PK analyses will be conducted using the PK Set.

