- n ECG print-outs: within 15 min before infusion start, at 10 min after infusion start, and, in case of conversion from AF, within 1 min after conversion BUT before infusion stop. Diagnosis of AF (defined as absence of discrete P waves and an irregular ventricular rate) to be confirmed based on a 12-lead ECG. On Day 2 the ECG should be completed 24 h +/- 2 hours after infusion start.
- o Continued assessment to start 30 min before infusion. Holter to stop after the PK sampling at 8 h. Telemetry to continue for minimum 8 h after infusion start.
- p Should be done in all patients; mandatory if not done within 6 months (inclusive) before randomisation.
- q Heart rhythm, LV size, LV area, LVEF, atrial area and size as well as other clinically significant finding results to be provided or requested if available.
- r In case of AF persistence at 90 min after start of infusion, a direct-current electrical cardioversion is to be done within 180 min post-infusion start (200 J biphasic synchronised).
- s Recording of any AEs/SAEs will start after the ICF has been signed. From infusion start, special attention should be paid to AEs related to the central nervous system including tremors.

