8.4.8.2 Rescue Medication

All patients who will not convert from AF during infusion of the study drug or within 90 min after the infusion start should undergo DC electrical cardioversion within 180 min from the time the infusion started. DC electrical cardioversion should be performed using biphasic synchronised cardioverter with energy of 200 J.

All medications necessary for direct-current electrical cardioversion (e.g. sedatives) should be administered per local standards, observing limitations from [Section 8.4.8.1](#) (Prohibited Medication and Procedures), and should be recorded as concomitant medications.

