9.4 Day 1 – Post-Infusion

The following procedures will be performed post-infusion on Day 1:

- Record any AEs that have occurred and any changes in concomitant medication since the infusion. Special attention should be paid to monitoring for AEs related to the central nervous system including tremors.
- Record vital signs ([semi]supine BP, heart rate, heart rhythm from ECG). Should be recorded before an electrical cardioversion, if applicable.
- Collect PK plasma samples at 45 min \pm 5 min, 1 h \pm 5 min, 1 h 30 min \pm 5 min, 4 h \pm 5 min, and 8 h \pm 5 min after start of infusion.
- Continue 12-lead Holter monitoring until after the 8 h PK sample is collected.
- Perform telemetry until at least 8h after infusion start.
- Do electrical cardioversion in case of AF persistence (refer to the Schedule of Assessments in [Section 8.1.2](#) for exact timing and parameters).

Prior to discharge of the patient, the Day 2 follow-up visit will be scheduled.

9.5 Day 2

The following procedures will be performed on Day 2:

- Record any AEs that have occurred since Day 1 and any changes in concomitant medication. Special attention should be paid to monitoring for AEs related to the central nervous system including tremors.
- Record vital signs (BP, heart rate, heart rhythm from ECG).
- Collect blood samples for clinical chemistry (refer to the Schedule of Assessments in [Section 8.1.2](#) for parameters included).
- Collect PK plasma samples 24 h ± 2 h after start of infusion.
- Perform a 12-lead ECG 24h ± 2 h after start of infusion.

The Day 30 follow-up visit will be scheduled.

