6.4. Visit Windows

Not applicable

This document is confidential.

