8.2. Secondary Efficacy Endpoint(s) and Analyses

8.2.1. Time to conversion from AF from start of infusion

The time to conversion from AF from start of infusion will be analysed using Kaplan-Meier methods. The number of patients that reached cardiac conversion within 90 mins of start of study drug infusion will be summarized using the median time to cardiac conversion along with the interquartile range (IQR).

A Kaplan Meir plot stratified by treatment group will be presented. A logrank test will be used to compare treatment groups.

Time to conversion (in min) will be calculated using the formulae:

This document is confidential.

Time to conversion (in min) = (Time of conversion or censoring - time of start of infusion).

In case of AF persistence at 90 min after start of infusion, a direct-current (DC) electrical cardioversion is to be done within 180 min post-infusion start. Patients who have electrical cardioversion will be censored. The time of censoring will be 90 min.

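### The 3 h ± 1 h sinus-rhythm window overlaps the DC-cardioversion window, and nothing fixes whether a non-converter is read before or after the shock

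*SAP*

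**What the plan says.** The proportion in SR at 3 h ± 1 h after start of infusion is a secondary efficacy endpoint (Protocol 7.2.2.1 and 11.1.3, SAP 4.2). SAP 8.2.3 analyses "The proportion of patients in SR after start of infusion at different timepoints" by logistic regression on treatment and AF duration. It does not say how a patient who has had DC cardioversion is classified.

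On rescue, the Protocol 8.1.2 footnote says that "direct-current electrical cardioversion is to be done within 180 min post-infusion start" when AF persists at 90 min. Protocol 8.4.8.2 says such patients "should undergo DC electrical cardioversion within 180 min from the time the infusion started". SAP 8.2.1 repeats the trigger, "In case of AF persistence at 90 min after start of infusion", and uses it to censor time to conversion at 90 min. SAP 8.2.2 adds a pharmacological-only repeat for IRAF. SAP 8.2.3 has no counterpart to either rule.

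On which rhythm reading counts:
- Protocol 10.1.1.1 bases the secondary efficacy endpoints on Holter and site ECGs.
- The scheduled 12-lead print-outs (Protocol 8.1.2) are pre-infusion, at 10 min, at conversion and at 24 h.
- Holter extractions follow the PK times, which go from 1 h 30 min to 4 h.
- Post-infusion vital signs include heart rhythm, and Protocol 9.4 adds: "Should be recorded before an electrical cardioversion, if applicable".
- SAP section "6.4. Visit Windows" is marked as not applicable.

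**The concern.** The SR window opens while shocks are still being given. A patient shocked at 150 min is in AF at 130 min and, if the shock works, in SR at 170 min. Both readings satisfy 3 h ± 1 h, so the recorded outcome turns on when the site shocked and when the rhythm was read. The permitted sources can also fall on opposite sides of the shock: the vital-signs rhythm is taken before it by instruction, while a Holter reading late in the window comes after it.

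The effect is largest in the arm with most non-converters, which one would expect to be placebo. At stake is a named secondary endpoint with a planned between-arm comparison. Its table (14.2.2.3.1) is also marked for delivery at the interim analyses.

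**Working it through.** The documents give no expected rate, power or sample size for this endpoint, so there is no plan figure to reproduce. The check is interval arithmetic followed by an illustration.

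**Overlap.** SR window: (3 − 1) × 60 = 120 min to (3 + 1) × 60 = 240 min. DC window: 90 to 180 min. The intersection is 120 to 180 min. That is 60 min, or 60/120 = 50% of the SR window and 60/90 = 67% of the DC window. A patient shocked between 90 and 120 min is post-shock throughout the SR window. A reading from 180 min on is post-shock if DC was on schedule. The ambiguity therefore concerns patients shocked after 120 min and read before 180 min.

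**Inputs for size.**
- Conversion rates p, from the simulated final data in Protocol 17.3 Example 1: placebo 6/42 = 0.143; 5 mg/kg 28/36 = 0.778.
- DC success s: assumed 0.9, range 0.7 to 1.0.
- Timing: assumed, with the shock uniform on 90 to 180 min.
- No relapse, and SR counted by any route.

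**Share read before the shock, b.** For a reading at time t between 120 and 180 min, the chance that the shock is still to come is (180 − t)/90. Its average over 120 to 180 min is 30/90 = 1/3.
- Reading uniform on 120 to 180 min: b = 1/3 (33%).
- Reading uniform on 120 to 240 min: half the readings are after 180 min, so b = 1/2 × 1/3 = 1/6 (17%).
- Reading fixed at 180 min: b = 0.

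**Arm rate and difference.** SR rate = p + (1 − p)(1 − b)s. With b and s common to the arms, difference = (0.778 − 0.143) × [1 − (1 − b)s] = 0.635 × [1 − (1 − b)s].

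At s = 0.9:

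| Share read before shock | Placebo | 5 mg/kg | Difference |
|---|---|---|---|
| 0 | 0.914 | 0.978 | 0.635 × 0.10 = 0.063 |
| 1/6 | 0.786 | 0.944 | 0.635 × 0.25 = 0.159 |
| 1/3 | 0.657 | 0.911 | 0.635 × 0.40 = 0.254 |
| 1 (extreme) | 0.143 | 0.778 | 0.635 |

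Difference in points over the assumed range of s:

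| s | b = 0 | b = 1/6 | b = 1/3 |
|---|---|---|---|
| 0.7 | 19 | 26 | 34 |
| 0.8 | 13 | 21 | 30 |
| 0.9 | 6 | 16 | 25 |
| 1.0 | 0 | 11 | 21 |

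The last row of the first table needs every shock to fall after 120 min and every reading to come before it. It is a bound, not an expectation.

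**The case against.** **The nominal time is 180 min, which is also the DC deadline.** If sites read at nominal 3 h and shock on schedule, nobody is read early and the problem disappears. That is correct, but the plan states a window of ± 1 h and schedules no ECG or Holter extraction at 3 h. The rule in SAP 6.1 that takes the first non-missing value covers repeats at a scheduled visit, and there is no 3 h visit.

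**The Holter runs continuously for about 8 h, so the data can settle it.** This stands, and it is why the fix is cheap. Having the recording does not choose the reading, however. SAP 10.6 mentions a separate cardiac SAP, but under safety ECGs. Neither document says that it defines this endpoint.

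**The real gap is the missing DC rule.** If DC recipients counted as not in SR, a shocked patient would fail whichever reading was used. This largely stands: the two questions are linked. But SAP 8.2.3 does not say so, and the endpoint as worded is simply being in SR. On that reading the timing matters.

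**Stronger readings that a reader might infer.** One is that the arm difference reflects timing instead of the drug. The formula does not support that. The drug effect is multiplied by a common factor between 0 and 1, so it shrinks but keeps its sign. Assessors are blinded (Protocol 8.4.7), and nothing in the documents suggests that shock or reading times would differ by arm. Another is that this figure drives dose selection. Protocol 11.1.6 and SAP 11 base the algorithm and the dose increase or decrease on AF conversion only. The DMC does receive the table, and Protocol 11.1.6 also lets it weigh other available data, so it may see an unstable number. No dose rule uses that number.

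**Conclusion.** The concern holds as a defect in a secondary endpoint. The 120 to 240 min SR window and the 90 to 180 min DC window overlap for 60 min, and no provision in either document says which reading counts for a patient shocked after 120 min.

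With Example 1 rates and 90% DC success, the arm difference is about 6 points with all readings post-shock and about 16 to 25 points under the two spread-out timing assumptions. The 64-point figure is only the extreme. These sizes rest on simulated rates, on DC success and timing that the documents do not give, on no relapse, and on counting SR by any route. The overlap itself rests on no assumption.

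The consequence is an unstable, diluted estimate, not a reversed one. The primary endpoint and time to conversion stop at 90 min and are untouched. The point is worth correcting before analysis, but it does not threaten the main conclusion.

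**What to change.** In SAP 8.2.3, with a cross-reference from 6.4:

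1. For every patient, take 3 h SR status from the continuous Holter at one fixed point inside the existing window and at or after the 180-min DC deadline, for example the first readable rhythm from 180 min, within 180 to 240 min.
2. State that the vital-signs rhythm recorded before cardioversion is not the source for this endpoint.
3. Flag any patient shocked later than 180 min, since that reading could still precede the shock.
4. Report the same endpoint with DC recipients counted as not in SR, as a drug-only status. This mirrors the pharmacological-only repeat in SAP 8.2.2. It is needed because a reading taken wholly after the shock is the one in which DC successes most hide the drug effect.

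The already planned extractions are poorer choices. The 4 h ± 5 min extraction can fall after 240 min and would relabel the endpoint. The 1 h 30 min ± 5 min extraction runs to 95 min and so can follow a shock given just after 90 min.

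The cost is one specified Holter reading per patient and one extra table. The endpoint stays within its stated window, no procedure is added, and DC timing is unchanged.

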3.3. Exploratory Objectives

The exploratory objectives of the study are as follows:

- To study demographic and echocardiographic variables, concomitant diseases, and concurrent medication with respect to the efficacy and safety of one or more dose levels of AP30663.
- To evaluate the PK of AP30663, including influence of dose, concomitant medication, concurrent diseases, and demographic variables.
- To explore the proportions of patients on AP30663 converting from AF and of patients randomised to placebo and converting at DC cardioversion.

[figure not shown]

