4.2. Secondary Efficacy Endpoints

- The time to conversion from AF from start of infusion.
- The proportion of patients with relapse of AF within 5 min (IRAF) following pharmacological or direct-current (DC) cardioversion.
- The proportion of patients in SR at $3\text{ h} \pm 1\text{ h}$ after start of infusion.
- The proportion of patients in SR at $24\text{ h} \pm 2\text{ h}$ after start of infusion.
- The proportion of patients in SR at $30\text{ days} \pm 5\text{ days}$ after start of infusion.

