Table 14.1.5.2	Compliance with Study Treatment	Safety Set	
Table 14.2.1.1.1	Conversion from AF within 90 Minutes from Start of Infusion : Summary of Response Rate, Bayesian Model	Full Analysis Set	✓
Table 14.2.1.1.2	Conversion from AF within 90 Minutes from Start of Infusion : Summary of Response Rate, Bayesian Model	Per Protocol Set	
Table 14.2.1.1.3	Conversion from AF within 90 Minutes from Start of Infusion : Summary of Response Rate, Logistic Regression	Full Analysis Set	✓
Table 14.2.1.1.4	Conversion from AF within 90 minutes from start of infusion : Summary of Response Rate, Logistic Regression	Per Protocol Set	
Table 14.2.2.1.1	Time to Conversion from AF – Descriptive Statistics, Kaplan-Meier Analysis	Full Analysis Set	✓
Table 14.2.2.1.2	Time to Conversion from AF – Descriptive Statistics, Kaplan-Meier Analysis	Per Protocol Set	
Table 14.2.2.2.1	Relapse of AF within 5 min following Pharmacological or DC Conversion – Summary of relapse rate - Logistic Regression	Full Analysis Set	
Table 14.2.2.2.2	Relapse of AF within 5 min following pharmacological or DC conversion – Summary of relapse rate	Per Protocol Set	

This document is confidential.

Table Number	Name	Analysis Set	Delivered for Interim analysis/DMC
Table 14.2.2.2.3	Relapse of AF within 5 min following Pharmacological Conversion – Summary of relapse rate - Logistic Regression	Full Analysis Set	
Table 14.2.2.2.4	Relapse of AF within 5 min following Pharmacological Conversion – Summary of relapse rate - Logistic Regression	Per Protocol Set	
Table 14.2.2.3.1	Proportion of Patients in SR after Start of Infusion at Different Timepoints - Logistic Regression	Full Analysis Set	✓
Table 14.2.2.3.2	Proportion of Patients in SR after Start of Infusion at Different Timepoints - Logistic Regression	Per Protocol Set	
Table 14.2.3.1	Descriptive Statistics of Plasma Concentration over Time by Treatment	PK Set	
Table 14.2.3.2	Summary of Pharmacokinetic Parameters – NCA Approach	PK Set	
Table 14.3.1.1	Overall Summary of Treatment-Emergent Adverse Events	Safety Set	✓
Table 14.3.1.2	Treatment-Emergent Adverse Events by System Organ Class and Preferred Term	Safety Set	
Table 14.3.1.3	Treatment-Emergent Adverse Events Related to Study Treatment	Safety Set	✓
Table 14.3.1.4	Serious Treatment-Emergent Adverse Events by System Organ Class and Preferred Term	Safety Set	✓
Table 14.3.1.5	Treatment-Emergent Adverse Events Leading to Study Discontinuation by System Organ Class and Preferred Term	Safety Set	

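### The SR comparisons in SAP 8.2.3 mix rhythm restored by drug with rhythm restored by DC shock, and no planned table separates the two

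*SAP*

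**What the plan says.** - **Rescue.** Protocol 8.1.2, footnote r: "In case of AF persistence at 90 min after start of infusion, a direct-current electrical cardioversion is to be done within 180 min" of infusion start. Protocol 8.4.8.2 repeats it: non-converters "should undergo DC electrical cardioversion within 180 min from the time the infusion started". Both apply to every arm.
- **SR endpoints.** SAP 4.2 lists SR at 3 h ± 1 h, 24 h ± 2 h and 30 days ± 5 days. Under SAP 8.2.3 these "will be presented by treatment group and analysed using a logistic regression model", with treatment and AF duration as the only terms. DC is not mentioned.
- **Neighbouring endpoints.** For time to conversion, SAP 8.2.1 states: "Patients who have electrical cardioversion will be censored. The time of censoring will be 90 min". For IRAF, the SAP 4.2 definition names the route: "The proportion of patients with relapse of AF within 5 min (IRAF) following pharmacological or direct-current (DC) cardioversion". SAP 8.2.2 then adds that "the same analysis will be done for the proportion of patients with relapse of AF within 5 min (IRAF) following pharmacological cardioversion only".
- **Outputs.** SAP section 16 has two SR tables (14.2.2.3.1 for the Full Analysis Set, 14.2.2.3.2 for the Per-Protocol Set), both titled "Proportion of Patients in SR after Start of Infusion at Different Timepoints - Logistic Regression". The first is marked for the interim analyses and the DMC. Neither is split by route.
- **Related objective.** SAP 3.3 includes: "To explore the proportions of patients on AP30663 converting from AF and of patients randomised to placebo and converting at DC cardioversion". No table is named for it.

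**The concern.** All three SR time points follow the rescue period or overlap it. If shock usually works, most placebo patients will also be in SR soon afterwards. A small or null SR difference could then mean that the drug effect did not last, or simply that placebo patients were rescued. The planned SR tables cannot tell these apart.

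SR supplies three of the five secondary efficacy endpoints, and its table goes to the DMC. The IRAF section shows that the authors saw the value of isolating the pharmacological route, but SR has no counterpart.

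The 3 h point has a further difficulty. Its window, 120 to 240 min, overlaps the period in which DC may be given (90 to 180 min). Protocol 9.4 asks for post-infusion vital signs, including rhythm from ECG, before any electrical cardioversion. Protocol 10.1.1.1 bases the secondary endpoints on both Holter and site ECGs. A site reading before the shock and a Holter reading after it could therefore classify the same patient differently. The general rule in SAP 6.1 takes the first of repeated post-infusion measurements, but it does not refer to DC or choose between the two sources.

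**Working it through.** **Text check.** DC handling for each conversion or rhythm endpoint:

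| Endpoint | DC rule in the SAP | Output by route |
|---|---|---|
| Time to conversion (8.2.1) | Censored at 90 min | Not needed |
| IRAF (8.2.2) | Both routes, then pharmacological only | Tables 14.2.2.2.1 to 14.2.2.2.4 |
| SR at 3 h, 24 h, 30 days (8.2.3) | None stated | None |

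Protocol 7.2.2.1 and 11.1.3 do not fill the gap. SAP 6.6 plans no subgroups. Listing 16.2.6.1 covers conversion by patient but is not a summary.

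**Illustration of size.** The plan gives no SR rate, effect size or power, so there is no SR figure to reproduce. As a check on the borrowed inputs, Pr(P₅ > 0.65) for 28/36 under Beta(29, 9) is 0.941, matching the protocol's 0.94.

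Inputs:
- p, conversion without DC: 28/36 on Dose 5 and 6/42 on placebo (simulated Example 1, Protocol 17.3).
- s, shock success: not in the documents; assumed 0.50, 0.80 and 0.95.
- m, share of converters still in SR: assumed 1 (near the 3 h point), equal by route.

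Formulas: SR = m[p + (1 − p)s]. Share of SR by shock = (1 − p)s / [p + (1 − p)s]. The difference is therefore m(1 − s) × (28/36 − 6/42) = m(1 − s) × 0.635.

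| s | SR, Dose 5 | SR, placebo | Difference | By shock, Dose 5 | By shock, placebo |
|---|---|---|---|---|---|
| 0 | 28/36 = 0.778 | 6/42 = 0.143 | 0.635 | 0 | 0 |
| 0.50 | 32/36 = 0.889 | 24/42 = 0.571 | 0.317 | 4/32 = 12.5% | 18/24 = 75% |
| 0.80 | 34.4/36 = 0.956 | 34.8/42 = 0.829 | 0.127 | 6.4/34.4 = 19% | 28.8/34.8 = 83% |
| 0.95 | 35.6/36 = 0.989 | 40.2/42 = 0.957 | 0.032 | 7.6/35.6 = 21% | 34.2/40.2 = 85% |

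With m = 0.7 at a later time point, the differences become 0.22, 0.09 and 0.02. The shares by shock do not change, because m cancels.

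**What an analysis of SR without DC would show.** At m = 1 it gives 0.778 vs 0.143, which is the 90-min result again. At m = 0.7 it gives 0.54 vs 0.10, a difference of 0.44 with about 4 placebo events (0.10 × 42). Durability among those converted without DC rests on 28 and 6 patients. If 20/28 and 4/6 remained in SR, the Clopper-Pearson 95% intervals would be 0.51–0.87 and 0.22–0.96. That supports description only.

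**The case against.** The best defence is that being in SR at a time point is a state read from an ECG. Sections 8.2.1 and 8.2.2 need DC rules because they analyse conversion and relapse events. Since the SAP says so where DC is treated differently, silence in 8.2.3 naturally means that all routes count. This stands: stating it is a clarification, not the repair of an error.

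Several stronger readings are tempting, but the documents do not support them.
- **That the SR analysis is invalid or loses planned power.** The shrinkage comes from the rescue design together with an endpoint that ignores route. No power is claimed for SR, and relabelling the analysis would not change its difference.
- **That the DMC cannot see the rescue at all.** Table 14.2.1.1.1 (90-min conversion) and Table 14.2.2.1.1 (Kaplan-Meier, DC patients censored at 90 min) are also marked for the DMC. They show by arm roughly how many patients went to shock. If the IRAF denominators are converters, which is not stated, subtracting one IRAF table from the other would also give DC conversions. What is missing is SR crossed with route.
- **That the dose decisions or the primary endpoint are affected.** The primary endpoint closes at 90 min, and SAP section 11 bases the algorithm on AF conversion alone.
- **That the SR time points have no windows.** SAP 6.4 reads as not applicable, but 8.2.3 states the windows itself. Holter runs for at least 8 h, so rhythm at the nominal 180 min, when DC is due to have been done, can be read. Only the order of the 3 h reading and DC is left open.
- **That a clean comparison of SR without DC is available at Day 30.** The schedule lists electrical cardioversion on Day 1 only, the Day 30 procedures in Protocol 9.6 do not name it, and Protocol Table 2 restricts class I and III drugs only until the Day 2 visit is completed. Later cardioversion or drugs could contribute to SR.

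**Conclusion.** The point holds as a worthwhile, inexpensive improvement. The planned SR analysis is legitimate under its plain reading, but it cannot distinguish SR reached without a shock from SR reached by one, and no listed table does so. On the illustrative inputs the SR difference is 0.32 to 0.03, against 0.63 before rescue, and most placebo SR is by shock. These figures rest on simulated example data, an assumed shock success of 50–95%, and equal maintenance by route; they show direction and scale and do not predict the trial's result. The gap confined to the 3 h reading and the missing table for the exploratory objective are smaller parts of the same point. The cardiac SAP and the DMC Charter were not available, but SAP 8.2.3 does not refer to either for SR.

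**What to change.** In SAP 8.2.3, before unblinding:

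1. Keep the planned logistic regressions and label them as SR regardless of DC cardioversion.
2. Add one descriptive table of SR at each time point by treatment and Day 1 route: converted without DC, converted at DC, neither. State where a patient belongs who converts, relapses and is then shocked. The same table reports DC conversion in placebo patients for the exploratory objective in SAP 3.3.
3. Optionally, following 8.2.2, add a supplementary analysis of SR without Day 1 DC at 3 h and 24 h, labelled as largely carrying the 90-min difference forward. At Day 30 keep the route split descriptive, and note that later cardioversion or antiarrhythmic drugs may contribute.
4. For the 3 h point, flag whether each reading was before or after DC.

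**Cost.** One sentence, one table, up to two optional models, and an entry in SAP section 12, which now lists no changes. DC status is already needed for the censoring in 8.2.1; the flag also needs the time of DC. No visits or patients are added, and rescue treatment does not change. The drawback is small cells: on the Example 1 figures only 6 placebo patients convert without DC, so the table can describe durability but not test it.
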